6.4 Pregnancy

If, following initiation of the investigational product, it is subsequently discovered that a study subject is pregnant or may have been pregnant at the time of study exposure, including during at least 5 half-lives after product administration, the investigator must immediately notify the Sponsor or designate of this event and complete and forward a Pregnancy Surveillance Form to the BMS designate within 24 hours of awareness of the event and in accordance with SAE reporting procedures described in [Section 6.1.1](#).

In most cases, the study drug will be permanently discontinued in an appropriate manner (e.g., dose tapering if necessary for subject safety). Please call the Sponsor or designate within 24 hours of awareness of the pregnancy.

The investigator must immediately notify the Sponsor or designate of this event and complete and forward a Pregnancy Surveillance Form to Sponsor or designate within 24 hours of awareness of the event and in accordance with SAE reporting procedures described in [Section 6.1.1](#).

Follow-up information regarding the course of the pregnancy, including perinatal and neonatal outcome, and where applicable, offspring information must be reported on the Pregnancy Surveillance Form.

Any pregnancy that occurs in a female partner of a male study participant should be reported to Sponsor or designate. In order for BMS to collect any pregnancy surveillance information from the female partner, the female partner must sign an informed consent form for disclosure of this information. Information on this pregnancy will be collected on the Pregnancy Surveillance Form.

6.5 Overdose

An overdose is defined as the accidental or intentional administration of any dose of a product that is considered both excessive and medically important. All occurrences of overdose must be reported as an SAE (see [Section 6.1.1](#) for reporting details.).

6.6 Potential Drug Induced Liver Injury

Wherever possible, timely confirmation of initial liver-related laboratory abnormalities should occur prior to the reporting of a potential DILI event (see [Appendix 6](#) flow chart for sustained elevated liver safety abnormalities). All occurrences of potential DILIs, meeting the defined criteria, must be reported as SAEs (see [Section 6.1.1](#) for reporting details).

Potential drug induced liver injury is defined as:

1. Aminotransaminases (AT) (ALT or AST) elevation > 3 times upper limit of normal (ULN)
AND
2. Total bilirubin > 2 times ULN, without initial findings of cholestasis (elevated serum alkaline phosphatase),
AND
3. No other immediately apparent possible causes of AT elevation and hyperbilirubinemia, including, but not limited to, viral hepatitis, pre-existing chronic or acute liver disease, or the administration of other drug(s) known to be hepatotoxic.

6.7 Other Safety Considerations

Any significant worsening noted during interim or final physical examinations, electrocardiogram, x-ray filming, or any other potential safety assessment required or not required by protocol should also be recorded as a nonserious or serious AE, as appropriate, and reported accordingly.

7 DATA MONITORING COMMITTEE AND OTHER EXTERNAL COMMITTEES

An Independent Data Monitoring Committee (IDMC) will be established to monitor data on an ongoing basis to ensure the continuing safety of patients enrolled in this study, to ensure the integrity of the blinded nature of the study, and to oversee the planned interim analyses. An IDMC charter will be developed which will specify the roles and responsibilities of the members and interim decision rules. Sponsor Steering Committee will receive and act on the recommendations from the IDMC. A firewall will be established to ensure the maintenance of the study blind for the Sponsor, the investigational site staff, and study patients and their study partners.

Data summaries and listings will be provided to the IDMC to facilitate their safety assessment at the regularly scheduled times on an ad hoc basis if needed. The safety review includes serious adverse events and events of special interest, focusing on early signal detection. Further details on the frequency, content and methods of data reports to the IDMC will be outlined in the Charter of that Committee along with the processes and procedures the committee will follow.

8 STATISTICAL CONSIDERATIONS

8.1 Sample Size Determination

The sample size calculation is driven by several considerations.

The first consideration is to compare the response rate in PASI-75, the proportion of subjects with moderate to severe psoriasis experiencing a 75% improvement reduction in psoriasis area and severity index (PASI) score after 12 weeks, between BMS-986165 and placebo arms. With a one-sided, two-sample Fisher's exact test at significant level 0.05, a sample size of 42 per arm will provide at least 99% power to detect 50% increase in the PASI-75 response rate in an active

arm (i.e., 60% response rate) compared to the placebo assuming the response rate is 10% in the placebo arm.

The second consideration is to assess the response rate in PASI-75 in active dose arms. Data from 42 treated subjects per arm will produce a two-sided 95% confidence interval with a margin of error at most 15.1% (half width) using normal approximation.

The third consideration is to compare the response rates in PASI-75 in two active arms. With one-sided, two-sample Fisher's exact test at significant level 0.05, 42 subjects per arm will provide at least 82% power to detect at least 30% difference in the response rate in PASI-75 between any two active dose arms.

The proposed sample size is mainly driven by the third consideration. In addition, administration of BMS-986165 to 42 subjects in each active treatment group provides 34%, 88%, and 99% probability of observing at least one occurrence of any adverse event that would occur with 1%, 5%, or 10% incidence rate respectively.

8.2 Populations for Analyses

- All Enrolled Subjects: All subjects who sign an informed consent.
- All Randomized Subjects: All subjects who are randomized to a treatment. Subjects will be analyzed as per randomized treatment. All efficacy analyses will be performed using this population.
- All Treated Subjects: All subjects who have received at least one dose of study treatment. This population will be used for safety analyses and will be analyzed as per actual treatment received.
- Biomarker Analysis Population: All subjects that receive any study medication and have at least 1 post-treatment biomarker measurement.
- Pharmacokinetic Population: All subjects who receive any study medication and have any available concentration-time data.

All subjects who receive study drug will be included in the safety data set. All available data from subjects who receive BMS-986165 will be included in the pharmacokinetic data set. All available data from subjects for whom pharmacodynamic measurements are available at baseline and at least one other time will be included in the pharmacodynamic data set.

Summary analyses of safety, pharmacokinetic, pharmacodynamic, biomarker, and efficacy data will be based on all treated subjects. For analyses such as PK parameter estimations, the analyses will be based on all treated subjects with adequate data.

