6.3 Populations for Analyses

The following subject populations will be considered in this trial:

- All Enrolled Subjects: All subjects who sign an informed consent.
- All Randomized Subjects: All subjects who are randomized to a treatment.
- All Randomized and Treated Subjects: All randomized subjects who receive at least one dose of the study medication. Subjects will be grouped according to the treatment to which they are randomized by IWRS at the start of the study.
- As-Treated Analysis Population: All subjects who have received at least one dose of study medication. Subjects will be grouped according to the treatment that they actually receive as opposed to the treatment to which they are randomized. Subjects will be grouped on an as-randomized basis unless the subject received the incorrect medication for the entire treatment period. In that case, the subject will be analyzed in the treatment group associated with the incorrect medication he/she receives.
- Efficacy Analysis Population: All Randomized and Treated Subjects.
- Biomarker Analysis Population: All subjects that receive any study medication and have at least 1 post-treatment biomarker measurement.
- Pharmacokinetic Population: All subjects who receive any study medication and have any available concentration-time data.
- Per-Protocol Population: All randomized subjects without relevant protocol deviations (Section 7.2.1). The primary efficacy analysis will be performed using this population if there are more than 10% of the study subjects with relevant protocol deviations.

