7.5 Efficacy

Unless otherwise specified, the efficacy data will be presented using the Efficacy Analysis population.

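### The protocol and the SAP give conflicting rules for the primary efficacy population, and the SAP drops never-dosed subjects without a stated reason

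*Protocol*

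**What the plan says.** **Protocol 8.2, list of populations.** For All Randomized Subjects: "Subjects will be analyzed as per randomized treatment" and "All efficacy analyses will be performed using this population". For All Treated Subjects (at least one dose): "This population will be used for safety analyses and will be analyzed as per actual treatment received".

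**Protocol 8.2, last paragraph.** "Summary analyses of safety, pharmacokinetic, pharmacodynamic, biomarker, and efficacy data will be based on all treated subjects".

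**SAP 6.3.** "Efficacy Analysis Population: All Randomized and Treated Subjects". That set is randomised subjects with at least one dose, and "Subjects will be grouped according to the treatment to which they are randomized by IWRS at the start of the study". SAP 7.5 makes it the default: "Unless otherwise specified, the efficacy data will be presented using the Efficacy Analysis population".

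**SAP 6.3, Per-Protocol Population.** "The primary efficacy analysis will be performed using this population if there are more than 10% of the study subjects with relevant protocol deviations". SAP 7.2.1 instead says that a per-protocol analysis excluding those subjects will be done for the primary endpoint. SAP 7.5.6 says that one may be done if at least 10% of the efficacy population have relevant deviations.

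SAP 2.4 records protocol amendments as not applicable. The SAP document history (Section 11) lists a change of confidence level, among others, but no change of population.

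**The concern.** The population sets the denominator of the primary endpoint, so each document should give one rule and the two should agree. Here the protocol contradicts itself within one section. The SAP then adopts a set that differs from the one the protocol assigns to every efficacy analysis. The available SAP text gives no reason for leaving out subjects who were randomised but never dosed. The SAP also has a sentence that, read literally, replaces the primary population once deviations pass a threshold.

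If this stays open until unblinding, the set behind the headline PASI-75 comparison could be settled after results are known, and any choice could be defended by citing one passage or another.

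**Working it through.** **1. Which passages conflict**

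| Source | Members | Grouping | Stated use |
|---|---|---|---|
| Protocol 8.2, All Randomized | all randomised | as randomised | all efficacy analyses |
| Protocol 8.2, last paragraph | all treated | not stated there | summary analyses, including efficacy |
| SAP 6.3 and 7.5 | randomised and dosed | as randomised | efficacy by default |
| SAP 6.3, Per-Protocol | randomised, no relevant deviation | not stated there | primary analysis if more than 10% deviate |
| SAP 7.2.1 and 7.5.6 | subjects with deviations excluded | as in the primary analysis (7.5.6) | separate analysis of the primary endpoint |

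Rows 1 and 2 clash, because a rule for all efficacy analyses leaves no efficacy summaries for another set. Rows 1 and 3 clash over never-dosed subjects. Rows 4 and 5 clash over whether the per-protocol set replaces the primary set or adds to it. Rows 2 and 3 contain the same people unless someone is dosed without being randomised.

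**2. The plan's own figures (Protocol 8.1; SAP 5)**

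Inputs: 42 per arm, one-sided Fisher's exact test at 0.05. By exact enumeration:
- 10% vs 60%: power 99.97% (stated: at least 99%).
- 30-point difference at its least favourable position, 35% vs 65%: power 82.6% (stated: at least 82%).
- 95% half-width at 50%: 1.96 × √(0.25/42) = 15.1% (stated: 15.1%).

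None of these figures is in dispute.

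**3. Effect of never-dosed subjects**

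The documents give no count, so assume k = 0 to 4 never dosed of 42 randomised per arm, response rates of 60% and 10% among the dosed, and never-dosed subjects counted as non-responders in the all-randomised set.

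- Rate in a 60% arm: 0.60 × (42 − k)/42. For k = 1 this is 58.6%, a fall of 1.4 points. With whole counts, 25/42 = 59.5% becomes 25/43 = 58.1%, also 1.4 points.
- Active-placebo difference with k in each arm: 0.50 × (42 − k)/42. The randomised-and-treated set keeps 50.0 points throughout.

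| k per arm | Difference, all randomised | Power 10% vs 60%: treated only / all randomised | Power 35% vs 65%: treated only / all randomised |
|---|---|---|---|
| 0 | 50.0 | 99.97% / 99.97% | 82.6% / 82.6% |
| 1 | 48.8 | 99.95% / 99.95% | 81.1% / 80.8% |
| 2 | 47.6 | 99.94% / 99.93% | 79.5% / 78.9% |
| 4 | 45.2 | 99.92% / 99.86% | 76.6% / 74.8% |

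One never-dosed subject per arm costs 50.0 − 48.8 = 1.2 points on the difference. Active-versus-active power falls below 82% with the first such subject per arm in either set. That loss comes mostly from having fewer dosed subjects, and the choice of set adds 0.3 points at k = 1 and 1.8 at k = 4.

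**4. Can the SAP handle never-dosed subjects?**

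- Binary endpoints: yes. The first rule in SAP 8.3.1 covers only subjects who stop after receiving medication. Its fallback sets any response that still cannot be determined to non-responder, which reaches never-dosed subjects.
- Change from baseline: no. SAP 8.2 and 8.5 anchor baseline and study day to the first dose, and SAP 8.3.2 relies on a repeated-measures model under missing at random. A never-dosed subject has no place in those models.

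**The case against.** The SAP is the more detailed document and its default is clear. Its set, grouped as randomised, is defensible in a double-blind trial. Randomisation takes place on Day 1 (SAP 2.2), after eligibility results are reviewed (Protocol 5.3), and the Day 1 morning dose is given at the site (Protocol 4.5). Never-dosed subjects should therefore be few, and failure to start should not depend on the assigned arm. All of this stands, and it limits the size of the point. It does not remove the contradiction. Protocol 8.4.2 leaves the details of tests and models to the SAP, but it does not hand over the choice of population, which Protocol 8.2 fixes.

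A reader might infer that the primary endpoint could be analysed by drug actually received. The documents do not support that. The protocol sentence on actual treatment names safety analyses as its use. The closing paragraph speaks of summary analyses and gives no grouping. The SAP groups efficacy by IWRS assignment and keeps its As-Treated population for exposure (7.4) and safety (7.6).

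A reader might also put the effect of regrouping one subject at 1/42 = 2.4 points. That holds the denominator fixed. From 25/42 (59.5%), moving one subject out or in gives 24/41 (58.5%), 25/41 (61.0%), 26/43 (60.5%) or 25/43 (58.1%), so at most about 1.5 points. From 4/42 (9.5%) the largest shift is to 3/41 (7.3%), about 2.2 points.

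**Conclusion.** The plan is wrong as written on this point: the passages that set the primary denominator contradict each other and cannot all be followed. The substantive differences are the unexplained exclusion of never-dosed subjects in the SAP and the per-protocol sentence in SAP 6.3.

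The numerical effect is probably small: about 1.4 points on a 60% arm per never-dosed subject, about 1.2 points on the difference for one per arm, and power against placebo essentially unchanged. These sizes rest on the plan's 60% and 10% rates, 42 per arm and an assumed 0 to 4 never-dosed subjects per arm. That no reason is given for the exclusion is a statement about the available text only, since parts of the SAP were removed or redacted. It would be too strong to say that there are three materially different primary populations, because the two treated sets should contain the same people.

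**What to change.** 1. In both documents, name All Randomized Subjects, grouped as randomised, as the primary set for PASI-75 and the other binary efficacy endpoints. State that never-dosed subjects are non-responders under the fallback in SAP 8.3.1.
2. Keep All Randomized and Treated Subjects, grouped as randomised, as a supportive set for the binary endpoints and as the set for the change-from-baseline models. Say in Protocol 8.2 that those models are an exception.
3. In the last paragraph of Protocol 8.2, delete efficacy from the list of data summarised on all treated subjects.
4. Reword the per-protocol sentence in SAP 6.3 so that the analysis is supportive and never replaces the primary one. Align its starting set and trigger with SAP 7.2.1 and 7.5.6: 6.3 starts from all randomised subjects and 7.5.6 from the efficacy population, and the trigger is more than 10% in one place and at least 10% in another.

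The cost is wording in the protocol and the SAP, with no new data and no change in sample size. The downside is that response rates fall slightly if any subject is never dosed.

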8.3 Endpoints

8.3.1 Primary Endpoint(s)

The primary efficacy endpoint is the proportion of subjects in the study experiencing a 75% reduction from baseline in the PASI score after 12 weeks.

The safety and tolerability of BMS-986195 will be assessed by the incidence, potential significance, and clinical importance of adverse events measured during multiple doses of BMS-986195 and up to 30 days after the last dose, as determined by medical review of adverse event reports, vital sign measurements, electrocardiograms (ECGs), and results of physical examination and laboratory tests.

8.3.2 Secondary Endpoint(s)

The secondary efficacy endpoints are

- the proportion of subjects at week 12 with PASI-50, PASI-75, PASI-90, PASI-100
- sPGA score, DLQI score and the proportion of subjects with moderate to severe psoriasis in each category of these endpoints after week 12 of treatment

The secondary endpoint to assess PK is Ctrough.

[REDACTED]

8.4 Analyses

8.4.1 Demographics and Baseline Characteristics

Frequency distributions of gender and race will be tabulated. Summary statistics for age, body weight, height, and Body Mass Index (BMI) will be tabulated. In addition, baseline disease activities will be tabulated by treatments using descriptive statistics.

8.4.2 Efficacy Analyses

Primary Efficacy Analyses

The primary endpoint, the proportion of subjects with moderate to severe psoriasis experiencing a 75% improvement reduction in PASI score after 12 weeks, will be analyzed by two-sample Fisher's exact test or Chi-square test to compare the response rates between each treatment group and placebo. Cochran-Mantel-Haenszel Chi-square test, stratified according to previous treatment with a biologic and/or region (Japanese vs rest of world), will be performed. The odds ratio (odd in a treatment group/odd in placebo) in the response rates and its corresponding two-sided 90% confidence interval (CI) will be provided when using Fisher's exact test or

Cochran-Matell-Haenszel Chi-square test. If Chi-square test is performed, the difference in the response rates and its corresponding two-sided 90% confidence interval (CI) will be provided.

In addition, point estimate and 90% asymptotic and exact two-sided confidence intervals will be provided for the proportion of subjects in PASI-75 in each group. A logistic regression model may be performed to incorporate some of the covariates if these covariate are assumed to impact the response rates. Details of the tests and models will be given in the statistical analysis plan.

Secondary Efficacy Analyses

Similar analyses as in primary efficacy analyses will be performed to compare any two active arms.

A logistic model will be conducted to detect a positive trend between treatment groups of BMS-986165.

The response rate in PASI-50, PASI-75, PASI-90, and PASI-100 will be summarized by treatment and time and will be analyzed using a repeated measure model when applicable. The same analyses will be conducted stratified by previous biologic treatment and/or region. The proportion of subjects with a sPGA score of “0” or “1” will be analyzed similarly to the primary analyses. sPGA, and DLQI Score from psoriasis subjects will be tabulated by treatment and time; the corresponding changes from baseline and percent change from baseline will be calculated and summarized.

For continuous secondary endpoints (e.g. PASI, etc), point estimates and two-sided 90% confidence intervals for mean change from baseline within each treatment group will be provided. For binary endpoints (PASI, sPGA, etc.), point estimates of the response rate and two-sided 90% confidence intervals will be provided using normal approximation within each treatment group.

In addition, a two-sided 90% confidence interval will be provided for the difference in the secondary efficacy endpoints between each active arm and the placebo arm at each visit. More analyses, such as analysis of covariance models with treatment group, use of previous biologic treatment, and baseline value included as covariates, may be performed on endpoints such as PASI score, sPGA score, DLQI, etc.

There will be no adjustment for multiplicity. All comparisons will be performed in a pre-specified hierarchical procedure starting from the highest dose arm to the lowest dose arm. If a comparison is not significant at level 0.05, all P-values in subsequent comparisons will be considered to be nominal and may be provided if applicable.

[REDACTED]

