2.2 Treatment Assignment

After completion of all screening evaluations, on Day 1, all eligible subjects will be randomly assigned to 1 of 6 treatment arms (BMS-986165, 3mg Q2D; BMS-986165, 3mg QD; BMS-986165, 3 mg BID; BMS-986165, 6mg BID; BMS-986165, 12mg QD; and Placebo) in an equal ratio.

Enrolled subjects meeting inclusion and exclusion criteria will be eligible to be randomized. Randomization numbers will be assigned prior to dosing. During the screening visit, the investigative site will call into the enrollment option of the Interactive Web Response System (IWRS) designated by BMS for assignment of a 5-digit subject number that will be unique across all sites. Enrolled subjects, including those not dosed, will be assigned sequential subject numbers starting with 00001, (e.g., 00001, 00002, 00003....00010). The patient identification number (PID)

will ultimately be comprised of the site number and subject number. Once it is determined that the subject meets the eligibility criteria following the screening visit, the investigative site will call the IWRS to randomize the subject. Randomization will be stratified by the use of previous treatment with a biologic (yes/no) and region (Japan vs rest of world).

Specific instructions (including an enrollment/randomization worksheet) for the central enrollment and randomization procedure using an IWRS will be provided to the site.

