3.2 Secondary

- To assess that the proportion of subjects experiencing a 75% reduction in PASI score in the most efficacious treatment group
- To compare the proportions of subjects experiencing a 75% reduction in PASI score between treatment groups
- To assess a positive trend between treatment groups of BMS-986165 and proportion of subjects experiencing a 75% reduction in PASI score after 12 weeks of treatment
- To assess clinical efficacy of BMS-986165 as measured by improvement in skin disease area and severity indices PASI-50, -75, -90 and -100 over time in subjects with moderate to severe psoriasis
- To assess a significantly higher proportion of subjects achieving Static Physician's Global Assessment (sPGA) score of "0" ("cleared") or "1" ("minimal") after 12 weeks of treatment with BMS-986165 than after 12 weeks of treatment with placebo
- To assess improvement by BMS-986165 in Dermatology Life Quality Index (DLQI)
- To assess the trough concentrations of BMS-986165 in subjects with moderate to severe psoriasis

[REDACTED]

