5 SAMPLE SIZE AND POWER

The sample size calculation is driven by several considerations.

The first consideration is to compare the response rate in PASI-75, the proportion of subjects with moderate to severe psoriasis experiencing a 75% improvement in PASI score after 12 weeks, between BMS-986165 and placebo arms. With a one-sided, two-sample Fisher's exact test at significant level 0.05, a sample size of 42 per arm will provide at least 99% power to detect 50% increase in the PASI-75 response rate in an active arm (i.e., 60% response rate) compared to the placebo assuming the response rate is 10% in the placebo arm.

The second consideration is to assess the response rate in PASI-75 in active dose arms. Data from 42 treated subjects per arm will produce a two-sided 95% confidence interval (CI) with a margin of error at most 15.1% (half width) using normal approximation.

The third consideration is to compare the response rates in PASI-75 in two active arms. With a one-sided, two-sample Fisher's exact test at significant level 0.05, 42 subjects per arm will provide at least 82% power to detect at least 30% difference in the response rate in PASI-75 between any two active dose arms.

The proposed sample size is mainly driven by the third consideration. In addition, administration of BMS-986165 to 42 subjects in each active treatment group provides 34%, 88%, and 99% probability of observing at least one occurrence of any adverse event that would occur with 1%, 5%, or 10% incidence rate respectively.

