7.5.1 Primary Efficacy Analysis

The algorithm for PASI scoring is provided in Section 8.1.1. The percentage change from baseline in PASI will be calculated using the following formula:

$$[(\text{PASI Score at Day 85} - \text{Baseline})/\text{Baseline}] * 100$$

For a subject, PASI-75 is 1 if the percentage change from baseline is less than or equal to -75%, i.e., the subject has greater than or equal to 75% improvement in PASI score comparing to baseline. Otherwise, PASI-75 is 0. Missing value for PASI-75 will be imputed and the imputation method is described in Section 8.3.1.

The following analyses will be provided:

- To compare the response rates between each treatment group and placebo, the PASI-75 at Day 85 will be analyzed by two-sample Fisher's exact test or Chi-square test based on the observed counts. The odds ratio (odds in treatment group/odds in placebo) and the

difference in the response rates and their corresponding two-sided 95% confidence intervals (CIs) will be provided.

There will be no adjustment for multiplicity. All comparisons will be performed in a pre-specified hierarchical procedure starting from the highest dose arm to the lowest dose arm. If a comparison is not significant at level 0.05, all p-values in subsequent comparisons will be considered nominal.

- For the primary efficacy endpoint, the proportion of subjects with moderate to severe psoriasis experiencing a 75% improvement in PASI score at Day 85 (PASI-75), the count and percentage of subjects with PASI-75, along with the 95% asymptotic and Clopper-Pearson exact two-sided CIs, will be provided in each treatment group.
- A logistic regression model analysis will be performed to evaluate the impact of treatments on PASI-75 at Day 85, with treatment group, age, gender, weight, BMI, baseline PASI score, use of previous biologic treatment, study region, and use of previous biologic treatment-by-study region interaction as covariates, if applicable.
- A bar chart of PASI-75 response rate at Day 85 by treatment group will be provided.

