7.5.2 Secondary Efficacy Analyses

7.5.2.1 PASI-75

The following analyses will be provided for PASI-75:

- The Cochran-Armitage trend test will be performed to assess a positive trend between treatment groups of BMS-986165 and proportion of subjects experiencing a 75% reduction in PASI score at Day 85.
- A repeated measures logistic regression model analysis will be performed using a generalized estimating equations (GEE) model. The model will be fitted with treatment, visit, and treatment-by-visit interaction as the fixed effects and measurements within each subject as the repeated measurements. The use of previous biologic treatment, study region, and use of previous biologic treatment-by-study region interaction will be added into the model as covariates.
- A longitudinal line plot of the response rate in PASI-75 grouped by treatment will be provided.

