7.5.4 Subgroup Analyses

To investigate the impact of study region (Japan vs rest of world) and the use of previous biologic treatment on the primary efficacy endpoint, subgroup analyses will be performed. The Cochran–Mantel–Haenszel Chi-square test on the response rates in PASI-75 at Day 85 will be conducted and the odds ratio (odd in a treatment group/odd in placebo) in the response rates and its corresponding two-sided 95% CI will be provided.

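### Dose trend in PASI-75: the SAP's Cochran-Armitage test, as specified, uses neither the randomisation strata nor baseline PASI and gives no trend estimate; an adjusted logistic trend model is a cheap, minor improvement

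*Protocol*

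**What the plan says.** The trend is a secondary objective in both documents. SAP 3.2 words it as follows (last word omitted): "To assess a positive trend between treatment groups of BMS-986165 and proportion of subjects experiencing a 75% reduction in PASI score after 12 weeks of".

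For the analysis, protocol 8.4.2 says: "A logistic model will be conducted to detect a positive trend between treatment groups of BMS-986165". It names no covariates, dose scores or estimate for that model. SAP 7.5.2.1 says: "The Cochran-Armitage trend test will be performed to assess a positive trend between treatment groups of BMS-986165", applied to PASI-75 at Day 85. It too names no strata, covariates or scores, and no slope.

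Three other parts of the SAP bear on this:

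- Section 2.2: "Randomization will be stratified by the use of previous treatment with a biologic (yes/no) and region (Japan vs rest of world").
- Section 7.5.1 already plans a logistic regression of PASI-75 at Day 85 "with treatment group, age, gender, weight, BMI, baseline PASI score, use of previous biologic treatment, study region" and the interaction of the last two. Treatment enters as a group, and no trend is taken from the model.
- Section 7.5.1 also reports, for each dose against placebo, "The odds ratio (odds in treatment group/odds in placebo) and the" rate difference, with 95% intervals. Section 7.5.4 adds a Cochran-Mantel-Haenszel analysis with its odds ratio and interval, under subgroup analyses.

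SAP 2.4 lists no protocol amendment. The SAP's version history does not mention the change of trend method.

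**The concern.** In a dose-ranging trial the shape of response across active doses is a main product. The formal trend analysis ends in a p-value. It can say that response rises with dose, but not how steeply or how precisely that is known. The effect sizes in the visible SAP text are each dose against placebo, and these do not combine into a slope with its own interval.

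The SAP is also uneven. Its logistic and repeated-measures models of PASI-75 include both stratification factors, and the Day 85 logistic model adds baseline PASI. The trend analysis of the same outcome at the same visit uses none of them. If those factors predict response, an adjusted analysis would use the 210 active-arm subjects (5 × 42) somewhat better.

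**Working it through.** **1. The plan's own power figures.** SAP 5 states: "With a one-sided, two-sample Fisher's exact test at significant level 0.05, a sample size of 42 per arm will provide at least 99% power" for 60% against 10%, and at least 82% for a 30-point difference between two active arms. Exact enumeration of the one-sided Fisher test with 42 per arm gives 99.97% for 60% vs 10%. For a 30-point difference the lowest value found is 82.6%, at 35% vs 65%. Both figures reproduce. The documents state no power for the trend test.

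**2. Does the change of test cost power?** Take the protocol's model without covariates: logit p = α + βs, where s is the arm's score. The score statistic for β = 0 is

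z = Σ(s − s̄)y / √[p̄(1 − p̄) Σ(s − s̄)²],

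which is the Cochran-Armitage statistic. In simulation the two tests agreed within 0.3 points of power in every scenario (table, columns 3 and 4). The swap costs nothing.

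**3. Comparison with an adjusted trend model.** Taken from the documents: five active arms of 42, one-sided 0.05, daily-dose scores 1.5, 3, 6, 12, 12. Assumed, because the documents give no values: the response rates, 40% prior biologic, 15% Japan, and log odds ratios for prior biologic / Japan / 1 SD of baseline PASI of 0/0/0 (none), −0.5/−0.3/0.3 (weak), −1/−0.5/0.5 (moderate) and −1.5/−1/1 (strong). Overall rates were held at the stated values. Covariates were drawn at random per subject. The adjusted model includes both factors, their interaction and baseline PASI. With 2,000 runs per row, the simulation error of each power figure is up to about 1 point.

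| Rates across arms (%) | Covariate effect | Cochran-Armitage | Unadjusted logistic | Adjusted logistic | Adjusted − CA |
|---|---|---|---|---|---|
| 40/44/50/60/60 | none | 77.9 | 77.8 | 77.4 | −0.5 |
| | weak | 75.1 | 74.9 | 76.2 | +1.1 |
| | moderate | 75.7 | 75.6 | 78.5 | +2.8 |
| | strong | 75.9 | 75.8 | 85.9 | +10.0 |
| 45/48/52/60/60 | none | 56.6 | 56.3 | 56.3 | −0.3 |
| | weak | 54.7 | 54.6 | 55.9 | +1.2 |
| | moderate | 56.2 | 56.2 | 60.6 | +4.4 |
| | strong | 54.6 | 54.4 | 65.2 | +10.6 |

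For rates 30/36/44/60/60 power is near its ceiling (97.6 to 98.1% unadjusted) and the gain is at most 1.9 points. A separate simulation with rates rising from 35 to 55%, and covariate effects from none to strong, gave Cochran-Armitage vs adjusted power of 67.4 vs 66.5, 68.3 vs 68.7, 67.7 vs 69.6 and 67.8 vs 71.5%, a change of −0.9 to +3.7 points.

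**4. What the missing estimate hides.** Suppose responders are 15, 17, 19, 21 and 23 of 42, with scores 1 to 5 (invented data). Then Σ(s − s̄)y = −30 − 17 + 21 + 46 = 20, p̄ = 95/210 = 0.452 and Σ(s − s̄)² = 42 × 10 = 420. So z = 20/√(0.452 × 0.548 × 420) = 20/10.2 = 1.96, one-sided p about 0.025: a positive trend. The logistic slope from the same data gives an odds ratio per step of 1.21 (95% CI 1.00 to 1.48). Over four steps the interval runs from about 1.0 to 4.7. The p-value alone does not show that range.

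**5. Scores.** Any trend analysis needs them, and neither document states them. The daily doses are 1.5, 3, 6, 12 and 12 mg, so 6 mg BID and 12 mg QD tie. For plateau rates of 40/55/60/60/60%, calculated Cochran-Armitage power is 51.6% with daily-dose scores, 58.4% with scores 1 to 5 and 64.0% with tied ranks 1, 2, 3, 4, 4. This choice can matter more than the adjustment does.

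**The case against.** The strongest reply is that little is lost. The objective is to assess a positive trend and the protocol's model was to detect one; neither promises a slope. Readers will see every arm's response rate with asymptotic and exact intervals, every dose against placebo, an adjusted logistic model and a bar chart. Exposure-response modelling is planned separately (protocol 8.4.8.1). All of that stands and limits the point to a reporting improvement in one secondary analysis.

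Three stronger readings are tempting and not supported:

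- *Replacing the logistic model loses power.* It does not, as step 2 shows. The loss exists only against an adjusted trend model that neither document specifies.
- *The dose-trend objective has no effect size at all.* Only the trend slope lacks one; each dose has its own estimates.
- *The test is invalid, or materially conservative.* Under randomisation the unadjusted test is valid. In 100,000 runs with stratum shares fixed per arm, its one-sided error was 5.13% with no covariate effect and 4.72% with the strongest effects assumed there. That is too small to matter.

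Nor is Cochran-Armitage inherently unable to take strata, since a stratified extension exists; the SAP just does not specify one. It is also fair to say that an odds ratio per step means little until the scores are fixed, so the fix has to include them.

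**Conclusion.** The point holds as a cheap improvement of minor severity. The SAP departs from the protocol's named method. The trend test it plans ignores the strata and baseline PASI, and the visible text plans no trend estimate with an interval. (Part of the SAP's efficacy section is redacted and cannot be judged.)

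The missing estimate is certain on the visible text and is the main reason to act. The power argument is secondary: about 0 to 4 points for null-to-moderate covariate effects, more if effects are strong (about 10 points in the two scenarios tabulated). These sizes rest on assumed response rates, stratum shares and covariate strengths. The primary comparison with placebo is unaffected.

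**What to change.** In SAP 7.5.2.1:

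- Fit a logistic model of PASI-75 at Day 85 over the five active arms, with a trend term, prior biologic use, region and baseline PASI.
- State the trend scores before unblinding, including how 6 mg BID and 12 mg QD are scored.
- Report the odds ratio per unit of score with its 95% CI.
- Keep Cochran-Armitage, with the same scores, as supportive.
- Record the departure from protocol 8.4.2 and the reason for it.

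This is a new covariate specification rather than a return to the protocol's model, which listed none, and the SAP should say so. It also differs from a contrast in the 7.5.1 model, which treats arms as categories and adds age, gender, weight and BMI.

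The cost is SAP wording and one extra model. The downside is up to about 1 point of power if none of the covariates is prognostic.
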